6.5.10 Follow-up Visit

The required Follow-up visit occurs 21 or 35 (+7 days) after the Week 10 visit or the last dose of study drug for subjects who discontinue study drug early. The required follow-up period is defined as a minimum of 3 weeks for those subjects who will enroll in the one-year open-label safety study on the date of the follow-up visit, and as 5 weeks for those subjects who will not be enrolled in the one-year open-label safety study of serlopitant. Should a subject present for the follow-up visit prior to 5 weeks after the last dose of study drug and be excluded from participation in the one-year study for any reason, the subject will be required to return at 5 weeks after the last dose of study drug for a complete follow-up visit.

At the Follow-up visit, the following procedures and assessments are to be performed:

- Register visit into the IWRS
- Ask the subject to complete the HADS and ESS questionnaires
- Assess and record any changes in the subject's concomitant medications
- Female subjects should be queried for presence of new breast masses or abnormal discharge, and abnormal vaginal bleeding or discharge
- Review menstrual diary and record dates of menstrual flow (if applicable)
- Obtain vital signs

- Perform targeted physical examination, including weight
- Perform IGA PN-A
- Perform IGA PN-S
- Obtain ECG
- Obtain photos (at selected sites, only subjects that signed photography consent)
- Perform a urine pregnancy test for females of childbearing potential (with positive or equivocal results confirmed by a serum pregnancy test)
- Draw blood for clinical laboratory tests (morning blood sampling due to Endocrine assessments)
 - Reproductive endocrine labs for females under 55 years of age at consent
 - Endocrine
 - Hematology
 - Chemistry
- Assess and record any AEs and SAEs
- Collect eDiary device, review eDiary for compliance

6.5.11 *Early Termination*

Early termination of a subject from the study may occur due to loss to follow-up or withdrawal of consent by the subject. In accordance with legal requirements and International Conference on Harmonization (ICH) –GCP guidelines, every subject or his/her legal representative has the right to withdraw from the study at any time and without providing reasons. If provided, the reason (adverse event, study burden, lack of efficacy, other) a subject withdrew consent will be recorded in the electronic Case Report Form (eCRF). The PI or site staff must make every effort to contact subjects who are suspected of being lost to follow-up. Attempts to contact such subjects must be documented in the subject's source documents.

7 ASSESSMENT OF SAFETY

7.1 Definitions

7.1.1 *Adverse Event*

An AE is any untoward medical occurrence associated with the use of a drug in humans, whether or not considered drug related. An AE can be any unfavorable and unintended sign (e.g. an abnormal laboratory finding), symptom, or disease temporally associated with the use of a drug, without any judgment about causality.

AEs include treatment emergent exacerbations of pre-existing illnesses and AEs that occur as a result of protocol-mandated interventions.

7.1.2 *Serious Adverse Event*

An AE is considered “serious” if it results in any of the following outcomes:

- Death
- Life-threatening AE (i.e. the subject was at immediate risk of death from the event as it occurred. An event that might have led to death if it had occurred with greater severity is not “life-threatening”)
- Inpatient hospitalization or prolongation of existing hospitalization
- Persistent or significant incapacity or substantial disruption of the ability to conduct normal life functions
- Congenital anomaly/ birth defect
- Important medical event (i.e. an event that may not result in death, be life-threatening, or require hospitalization, but which may be considered serious by the investigator or Sponsor, as it may jeopardize the subject and may require medical/surgical intervention to prevent one of the outcomes listed above). Examples of such medical events include allergic bronchospasm requiring intensive treatment in an emergency room or at home, blood dyscrasias or convulsions that do not result in inpatient hospitalization, or the development of drug dependency or drug abuse.

The following are not considered SAEs: a visit to the emergency room or other hospital department < 24 hours that does not result in admission (unless considered an important medical or life-threatening event), an elective surgery planned prior to signing consent, admission as per protocol for planned medical/surgical procedure, and/or routine health assessments requiring admission for baseline/trending of health status (e.g. routine colonoscopy).

The terms “severe” and “serious” are not synonymous. Severity refers to the intensity of an AE (e.g. mild, moderate, or severe pain); the event itself may be of minor medical significance (e.g. severe back pain). “Serious” is a regulatory definition, as defined above. Seriousness (not severity) serves as the basis for defining regulatory reporting obligations.

Severity and seriousness should be independently assessed when recording AEs and SAEs on the eCRF.

7.1.3 *Abnormal Physical Exam, Laboratory, Vital Sign, and Electrocardiogram Findings*

Abnormal physical exam findings that are clinically significant and are identified prior to the first dose of study drug should be recorded as medical history. New or worsening clinically significant abnormal physical exam findings identified after the first dose of study drug should be recorded as AEs.

Only abnormal laboratory, vital sign, and ECG findings that are considered clinically significant by the investigator (e.g. require active management or are associated with accompanying symptoms/signs) will be recorded as medical history or AEs on the eCRF. Abnormal laboratory, vital sign, and ECG findings that occur prior to the first dose of study drug should be recorded as medical history, and abnormal findings that occur after the first dose of study drug should be recorded as AEs.

If the clinically significant laboratory, vital sign, or ECG abnormality is a sign associated with a confirmed disease or condition (e.g. elevated creatinine in a subject diagnosed with chronic kidney disease), only the diagnosis (chronic kidney disease) needs to be recorded on the AE eCRF (rather than listing individual test findings as AEs).

Separate instances of the same clinically significant laboratory, vital sign, or ECG abnormality across visits should not be recorded as separate AEs or SAEs.

7.1.4 *Deaths*

Any deaths that occur from the time of informed consent to the follow-up visit, regardless of attribution, must be reported within 24 hours of investigator's awareness of the death. See Safety Form Completion Instructions for complete instructions.

The Sponsor should be provided a copy of any post-mortem findings and/or relevant medical reports, including histopathology.

7.1.5 *Pregnancies and Contraception Requirements for Females*

For the purposes of this study, a female of childbearing potential is defined as any female who has experienced menarche and is pre-menopausal, unless permanently surgically sterile (e.g., hysterectomy, bilateral salpingectomy, bilateral oophorectomy). A postmenopausal state is defined as no menses for 12 months without an alternative medical cause in a previously menstruating female.

For the purposes of this study, acceptable contraception is defined below based on *Nonclinical Safety Studies for the Conduct of Human Clinical Trials and Marketing Authorization for Pharmaceuticals: ICH M3(R2)* dated January 2010, and other available guidelines ([“U.S. Medical Eligibility Criteria for Contraceptive Use” 2010](#); [“Recommendations related to contraception and pregnancy testing in clinical trials” 2014](#); [“M3\(R2\) Nonclinical Safety Studies for the Conduct of Human Clinical Trials and Marketing Authorization for Pharmaceuticals” 2010](#)):

All female subjects of childbearing potential must use highly effective contraception, which includes the use of one or more of the following acceptable methods:

1. Surgical sterilization (e.g., bilateral tubal occlusion or ligation, hysterectomy, bilateral salpingectomy, bilateral oophorectomy)
2. Total (as opposed to periodic or cyclic) abstinence from heterosexual intercourse, only if planned for the entire duration of the study period and consistent with the preferred and usual lifestyle for the subject
3. Hormonal contraception associated with consistent inhibition of ovulation; these may include (but are not necessarily limited to) oral, intravaginal, implantable, injectable, or transdermal delivery methods
4. Intrauterine device/system
5. Exclusive (sole) monogamous intercourse with a sterilized (i.e., vasectomized) or otherwise non-fertile (e.g., castrated) male partner; the male partner must have received medical assessment of the surgical success

Progesterone-only oral contraceptives are excluded as a highly effective method of contraception, as they do not consistently inhibit ovulation. Male or female condoms with or without spermicide, and female caps, diaphragms, and sponges with spermicide, or combinations (double barrier) are also excluded as highly effective contraceptive methods.

Any pregnancy occurring in a female subject or the female partner of a male subject, from the first study drug administration through the required follow-up visit must be reported within 24 hours of the investigator's awareness of the pregnancy. See Safety Form Completion Instructions for complete instructions.

The investigator will follow the pregnancy to delivery or other pregnancy outcome.

Pregnancy in a female clinical trial subject or female partner of a male clinical trial subject is not an SAE per se. Complications of such pregnancies (for example, spontaneous abortion) may qualify as SAEs and should be reported as such even if they occur after the Follow-up visit. Any congenital anomalies/birth defects must be recorded and reported as SAEs. See Safety Form Completion Instructions for complete instructions.

7.1.6 *Worsening of Pruritus or PN*

Pruritus or PN should be recorded as an AE or SAE only if considered by the investigator to have worsened in severity beyond the subject's typical fluctuations. It is important to include a description of the nature of the unexpected worsening when recording the AE or SAE (e.g. new PN lesions in previously uninvolved skin).

7.2 Methods and Timing for Recording and Reporting Adverse Events

7.2.1 Adverse Event Reporting Period

Any AE occurrence during the study must be recorded on source documentation and eCRF at the site, in accordance with protocol instructions.

AEs and SAEs will be recorded from the first study drug administration through the follow-up visit. After the required follow-up visit, only SAEs that are believed to be drug-related should be reported.

After informed consent, but prior to initiation of study drug, only SAEs considered by the investigator to be caused by a protocol-mandated intervention will be collected (e.g. SAEs related to invasive procedures such as blood collection). These procedure-related SAEs should only be reported on the source documents and SAE form, not on the AE eCRF. Subjects who undergo screening procedures but are not randomized into the study will not have SAEs recorded in the clinical database.

7.2.2 Eliciting Adverse Events

Investigators will seek information on AEs and SAEs at each subject contact through the follow-up visit. All AEs and SAEs, whether reported by the subject or noted by authorized study personnel, will be recorded in the subject's medical record and on the AE eCRF page, and, if serious, on the SAE form. For each AE and SAE recorded, the investigator will make an assessment of seriousness, severity, and causality.

7.2.3 Assessment of Severity

All AEs entered into the eCRF will be graded for severity using the National Cancer Institute Common Terminology Criteria for Adverse Events (NCI CTCAE) v4.03 ([“Common Terminology Criteria for Adverse Events \(CTCAE\)” 2010](#)) to describe the maximum intensity of the adverse event.

If the AE cannot be found in the event-specific NCI CTCAE grading criteria, the investigator should use the definitions for Grade 1, 2, 3, and 4 in [Table 1](#).

Table 1 Adverse Event Grading

Grade	Severity	Alternate Description ^a
1	Mild (apply event-specific NCI CTCAE grading criteria)	Asymptomatic or mild symptoms; clinical or diagnostic observations only; intervention not indicated.
2	Moderate (apply event-specific NCI CTCAE grading criteria)	Minimal, local or noninvasive intervention indicated; limiting age-appropriate instrumental activities of daily living (ADL ^b)
3	Severe (apply event-specific NCI CTCAE grading criteria)	Severe or medically significant but not immediately life-threatening; hospitalization or prolongation of hospitalization indicated; disabling; limiting self care ADL ^c
4	Very severe, life threatening, or disabling (apply event-specific NCI CTCAE grading criteria)	Life-threatening consequences; urgent intervention indicated.
5	Death related to AE	

^a Use these alternative definitions for Grade 1, 2, 3, and 4 events when the observed or reported AE is not in the NCI CTCAE listing. A semi-colon indicates ‘or’ within the alternate description of the grade.

^b Instrumental ADL refer to preparing meals, shopping for groceries or clothes, using the telephone, managing money, etc.

^c Self care ADL refer to bathing, dressing and undressing, feeding self, using the toilet, taking medications, and not bedridden.

Source: National Cancer Institute Common Terminology Criteria for Adverse Events (NCI CTCAE) v4.03

Note that severity, a measure of intensity, is not equivalent to seriousness, a regulatory definition of outcome. Regardless of severity, some AEs may meet the criteria for seriousness. See [Section 7.1.2](#) for the definition of an SAE.

If an adverse event changes in severity during the same study period (e.g., treatment period), only the highest severity grade will be recorded on the eCRF.

7.2.4 Assessment of Causality

The investigator’s assessment of causality must be provided for all AEs (serious and non-serious). An investigator’s causality assessment is the determination of whether there exists a reasonable possibility that the investigational product caused or contributed to an AE. Causality of an AE will be assessed by the investigator using the following terms:

- **Likely Related:** A reaction that follows a reasonable temporal sequence from administration of the study drug; that follows a known or expected response pattern to the suspected study drug; and for which other potential etiologies are considered less likely factors than the study drug.
- **Likely Unrelated:** A reaction that, considering all potential etiologies, is most likely due to factors other than the study drug.

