7.3 Follow-up of Adverse Events and Serious Adverse Events

The investigator must make every effort to follow all AEs and SAEs regardless of attribution until judged resolved or stabilized, the subject is lost to follow-up, or it has been determined that study drug treatment or participation in the study is not the cause of the AE or SAE.

7.4 Reporting Serious Adverse Events to the Sponsor and Institutional Review Board or Ethics Committee

The Sponsor or designee is under obligation to report certain SAEs to regulatory authorities related to investigational drugs in clinical trials. The Sponsor or designee must be notified within 24 hours of an AE when the investigator determines that an AE meets the protocol definition of an SAE, regardless of the cause or relationship to study drug.

An SAE related to study participation occurring before study drug administration and after informed consent should be promptly reported to the Sponsor. If the investigator learns of any SAE at any time after a participant has been discharged from the study, and the SAE is considered likely related to study drug, the SAE should be promptly reported to the Sponsor.

Please see the Safety Form Report Completion Instructions for safety reporting instructions.

The investigator must also comply with applicable requirements concerning reporting of SAEs to the IRB or Ethics Committee (EC). This may include initial or follow-up notification of an SAE or other safety information.

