7.5 Reporting Serious Adverse Events to Regulatory Authorities and Study Investigators

The Sponsor, or its designee, is responsible for submitting reports of serious, unexpected related adverse events to regulatory authorities on an expedited basis, according to the ICH E2A Guideline and to other regulatory authorities according to national and local regulations as required. The Sponsor, or its designee, is responsible for prompt submission to the IRB or EC of any expedited SAE reports submitted to regulatory authorities. All investigators participating in ongoing clinical studies with serlopitant will receive copies of the SAE reports submitted on an expedited basis to regulatory authorities.

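### Protocol 7.2.4's two causality terms do not carry out its own reasonable-possibility standard: a well-timed reaction of a new kind fits neither term, and a contributory one must be scored Likely Unrelated

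*Protocol*

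**What the plan says.** Protocol 7.2.4 requires a causality assessment for every AE and describes it as the "determination of whether there exists a reasonable possibility that the investigational product caused or contributed to an AE". It then offers two terms and no third.

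- **Likely Related** has three parts: plausible timing relative to dosing; a reaction "that follows a known or expected response pattern to the suspected study drug"; and the drug being a likelier explanation than any other candidate cause.
- **Likely Unrelated** applies when, with all candidate causes considered, the reaction "is most likely due to factors other than the study drug".

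The assessment, or something close to it, is used in these places:

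- **Protocol 7.4.** During the study every SAE goes to the sponsor within 24 hours, whatever its relationship. After discharge, an SAE the investigator learns of is to be reported if it is considered likely related.
- **Protocol 7.2.1.** After the required follow-up visit, "only SAEs that are believed to be drug-related should be reported".
- **Protocol 7.5.** The sponsor is "responsible for submitting reports of serious, unexpected related adverse events to regulatory authorities on an expedited basis".
- **Protocol 7.3.** All AEs and SAEs are followed irrespective of attribution until resolved or stabilised, the subject is lost, "or it has been determined that study drug treatment or participation in the study is not the cause of the AE or SAE".
- **SAP tables.** Those by relationship (14.3.1.1.5, 14.3.1.2.4.1 to 14.3.1.2.4.6, 14.3.1.3.3) have only the two rows. Table 14.3.1.1.1 also counts related TEAEs.
- **Protocol 8.3 and SAP 6.4.3.** Subjects who stop study drug because of a treatment-related AE are kept in the Per Protocol population.

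**The concern.** The section states one test and supplies categories that apply another. The stated test is wide: a reasonable possibility, and contribution is enough. The category Likely Related is narrow: the drug must be the leading candidate and the event must already be of a recognised kind. The pattern condition bears hardest on the events a safety system most needs to catch, those not seen before with this drug. It also sits badly with 7.5, which is aimed at unexpected reactions.

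At stake are the reporting of SAEs that surface after a subject has left the study, the meaning of the related-event columns in the safety tables, and the membership of one supportive efficacy population.

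**Working it through.** The plan states no figure on this point and none can be computed, so the check is a reading of the definitions followed by tracing the term through its uses.

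**Step 1: put four kinds of event through 7.2.4.**

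| Event | Stated test | Likely Related | Likely Unrelated | Result |
|---|---|---|---|---|
| Well timed, known pattern, no better cause | met | all three parts met | not met | Likely Related |
| Well timed, new kind, no better cause | met | fails on pattern | not met: other factors are not the most likely cause | no valid term |
| Well timed, drug plausibly contributes, another cause leads | met | fails on alternative causes | met | Likely Unrelated |
| No plausible link, another cause evident | not met | fails | met | Likely Unrelated |

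Rows 1 and 4 work. In row 2 the investigator must still answer, because causality is mandatory for every AE, but neither definition applies. In row 3 the definitions force an answer opposite to the stated test. The three parts of Likely Related are joined by a closing conjunction, so pattern is a condition and not an illustration.

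**Step 2: trace the consequences.**

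- **SAEs after discharge (7.4).** The trigger is the 7.2.4 term itself. A late SAE of the row 2 or row 3 kind, read literally, does not meet it. The unconditional 24-hour route covers on-study SAEs only, so here causality decides whether the sponsor hears of the event under 7.4.
- **SAEs after the follow-up visit (7.2.1).** The trigger is the investigator's belief, not the defined term. A row 2 event that the investigator attributes to the drug is reportable here. Sections 7.2.1 and 7.4 therefore set different tests for overlapping periods.
- **Expedited reports (7.5).** Related is required, but the section does not say whose judgement or which definition decides. On-study SAEs reach the sponsor in any case. The route is weakened if the sponsor adopts the investigator's term, and otherwise intact.
- **Follow-up (7.3).** The stop needs a determination that drug or participation is not the cause. Failing to qualify as Likely Related is not that determination. Only an event placed in Likely Unrelated could be argued to meet it.
- **Relationship tables.** Row 3 events are counted as unrelated. Row 2 events go wherever each investigator chooses, so the counts depend partly on individual habit.
- **Per Protocol population.** A subject who stops drug for a row 2 event scored Likely Unrelated, or for a row 3 event, is not covered by the retention clause, although the stated test in 7.2.4 is met.

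**The case against.** Several stronger readings are tempting, and the case against them is good.

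- **That new reactions are filed as Likely Unrelated by rule.** No such rule exists. A well-timed event with no better explanation fails that definition too. An investigator relying on the lead-in has as much textual basis for Likely Related.
- **That such events drop out of expedited reporting.** The documents do not show this. The sponsor receives every on-study SAE, 7.5 refers to the ICH E2A guideline and national rules, and nothing ties related in 7.5 to the investigator's term alone. Nor do the documents equate a known or expected pattern in 7.2.4 with the opposite of unexpected in 7.5.
- **That such events drop out of AE follow-up.** Section 7.3 starts from follow-up irrespective of attribution and ends it on causality only after a positive determination.
- **That a new signal would be hidden.** All AEs are recorded (Protocol 7.2.2), and the SAP tabulates TEAEs and serious TEAEs by arm with no relationship filter (SAP 6.9.2; Tables 14.3.1.1.2 and 14.3.1.3.1). The randomised comparison survives.
- **That the Phase 2 rates in Protocol 1.5.3 size the problem.** They count all SAEs and all related TEAEs. They do not say how many events were of a new kind, and the causality definitions used in that study are not given.

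It can also be said that the safety form instructions cited in 7.4, which are not among these documents, may tell investigators how to apply the terms. That may soften the problem in practice, but it does not cure protocol text that contradicts itself.

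All of this limits the consequences. None of it removes the conflict within 7.2.4 or the exposure of the post-discharge rule in 7.4.

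**Conclusion.** The point holds as an internal contradiction in Protocol 7.2.4 with bounded consequences. The two terms do not carry out the stated standard: one class of event has no valid term, and another is scored against the standard. Post-discharge SAE reporting under 7.4 is directly exposed. The related-event tables and the Per Protocol retention clause are affected. Expedited reporting may be weakened and is not shown to be lost.

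No numerical size can be given. The conclusion rests on three assumptions: that investigators apply the definitions as written, that related in the SAP tables and in the Per Protocol clause is taken from the 7.2.4 term, and that no unseen instruction overrides it. The ITT analysis of the primary endpoint does not use causality and is untouched. The correction is worth making because it is cheap and concerns the safety record.

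**What to change.** In Protocol 7.2.4, let both terms follow the standard the section already states:

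- *Likely Related*: there is a reasonable possibility that the study drug caused or contributed to the event.
- *Likely Unrelated*: there is no such reasonable possibility.

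Keep timing, known pattern and alternative causes as factors to weigh, and say that they need not all hold.

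Then reconcile the dependent sections with that wording: the different triggers in 7.2.1 and 7.4, the meaning of related in 7.5, and, within 7.3, the duty to follow irrespective of attribution against the causality-based stop. Which follow-up rule applies is for the sponsor to settle; the two clauses only need to agree. The SAP tables can keep their two rows.

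The cost is protocol and eCRF-guidance wording, with no change to dosing, visits or endpoints. Expect somewhat more events classed as related in both arms and possibly a few more expedited reports. Events already scored under the present definitions rest on a different basis, so whether to reassess them should be decided before unblinding.
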